# **9. Statistical Considerations**

## **9.1 Outcome Measures.**

### **9.1.1 Primary outcome**

Data – raw waveform data and their annotations – suitable for development of cerebral and renal autoregulation curves and pilot algorithms to predict cerebral desaturation.

### **9.1.2 Secondary outcomes**

- Agreement between MAP at the upper and lower limits of renal autoregulation from invasive and non-invasive blood pressure measurement.
- Agreement between MAP at upper and lower limits of cerebral autoregulation from invasive and non-invasive blood pressure measurement.
- Agreement between systolic, diastolic and mean arterial pressure derived from invasive and non-invasive measurements.

## **9.2 Sample Size.**

In this study data from 100 patients (50 per site) will be collected for the development of algorithms based on cerebral and renal oxygenation values and (non)invasive blood pressure measurements. Since no such algorithms have been developed

before, an estimate of 100 patients was made to start development and the data collected will power the next stage of development.

### **9.3 Interim Monitoring and Analyses.**

There is no planned interim analysis.

### **9.4 Analysis Plan.**

A full analysis plan will be written prior to data analysis however will include

- Descriptive variables (sex, age, length and bodyweight will be obtained, together with ASA status, medical history, medication use and baseline systolic, diastolic and mean blood pressure), timing and dosing of fluids and vasoactive drugs, surgery specific data (type of surgery, duration, use of epidural analgesia, estimated blood loss) and intraoperative hemodynamic data will be obtained. Continuous data will be presented as means and SD or medians and IQR, depending on the distribution of data. Missing data will be coded as missing and no imputation will be used.
- All intraoperative data will be presented as mean  $\pm$  sd or as median (IQR) according to their distribution. Missing data will be coded as missing and no imputation will be used.
- Cerebral and renal autoregulation curves will be created using invasive mean arterial pressure as a substitute of cerebral/renal perfusion pressure. Cerebral/renal oxygenation will be used as a surrogate of blood flow.
- Bland-Altman plot will be used to assess agreement and the limits of agreement between both methods
- Multiple linear regression will be used to estimate the effect of demographic variables (age, gender), medical history (diabetes, hypertension, and prior cerebrovascular accident), preoperative blood pressure (MAP, systolic blood pressure, pulse pressure), and time-averaged cerebral oximetry index characteristics on MAP at the LLA.
- Descriptive statistics will be used to present oxygenation data from the quadriceps muscle.

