## 1. Background

The brain has a high metabolic demand and receives about 12% of cardiac output (CO) (1). This high metabolic demand makes the brain at risk for injury when disturbances in hemodynamic status occur, e.g. during surgery. However, cerebral autoregulation is responsible for protecting the brain from injury caused by hemodynamic changes (2,3). The concept of cerebral autoregulation, including a lower limit, a plateau and an upper limit, was proposed in 1959 (4), which means that when cerebral perfusion pressure (CPP) is in the range between 50 and 150 mmHg cerebral blood flow (CBF), and hence oxygen delivery remains more or less constant by adjusting vascular resistance (3). A combination of myogenic, neurogenic, metabolic, and endothelial mechanisms are responsible for maintaining cerebral autoregulation (3). In case of an increase in CPP, local vasoconstriction occurs and in case of a decrease in CPP, vasodilatation occurs to maintain constant CBF. Cerebral perfusion pressure is calculated as mean arterial pressure (MAP) minus intracranial pressure and central venous pressure, and can be substituted by MAP when no elevation in intracranial pressure is suspected (5). When CPP or MAP reach values outside of the autoregulation range, CBF will become directly dependant on blood pressure resulting in decreased CBF and hence oxygen delivery which may result in postoperative neurologic complications.

Cerebral oxygenation as a surrogate of CBF in the assessment of cerebral autoregulation (5), can be measured by near-infrared spectroscopy (NIRS) and is increasingly used in the routine clinical care as cerebral oxygenation values have been associated with postoperative neurologic and general complications (6). The ForeSight Elite sensor technology allows for effective tissue interrogation by incorporating 5 wavelengths of near-infrared light to analyse tissue, providing a broad spectrum of NIRS wavelengths (685, 730, 770, 810, 870nm). This allows for effective tissue interrogation at points where oxygenated and deoxygenated haemoglobin are more greatly distinguished for highly accurate performance. The sensors are non-invasive and placed on the forehead and can measure tissue oxygenation to a depth of 2.5cm.

Using blood pressure measurements and by examining changes in cerebral oxygenation autoregulation curves can be created as well as upper and lower limits of autoregulation as has been previously performed (7–10). The trend in

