## **6. Treatment of Patient Participants**

When the participant arrives in the operating room they will be connected to standard monitoring including non-invasive blood pressure, ECG and SpO2. An arterial cannula (standard care) will be placed in a radial artery (brachial artery if radial is

unable to be cannulated) under local anaesthesia and connected to a FloTrac IQ transducer and haemodynamic data will be displayed on the Hemosphere platform. This monitor will be designated monitor 1. Subsequently, all study sensors will be applied. A Foresight sensor will be placed on the flank, above the kidney (localised by ultrasound) and one on the skin above the quadriceps, at a muscle dense location. Two sensors will be applied to the forehead and will be secured with a headband if necessary. The Foresight sensors will also be connected to the Hemosphere monitor 1. A ClearSight cuff will be placed on a suitable finger on the ipsilateral hand and connected to a second Hemosphere monitor, designated monitor 2. Both monitors will be synchronised for date and time.

A period of ten minutes will be used to capture baseline data before anaesthesia is induced. All treatment will be as per standard institutional care and none of the sensors will be used to guide treatment, except for the FloTrac sensor, which will be used according to routine clinical practice.

All interventions during the procedure including but not limited to fluid therapy, vasoactive drug administration and positional changes will be entered on to the hemosphere platform (monitor 1), and at the end of surgery, all data will be downloaded from each Hemosphere monitor.

Monitor 1 will provide measurements of cardiac output, cardiac index, stroke volume variation, stroke volume, stroke volume index, hypotension probability index, pulse rate, and systolic, diastolic and mean arterial pressure from the invasive arterial waveform and cerebral, renal and muscle tissue oxygen saturations.

Monitor 2 will provide measurements of cardiac output, cardiac index, stroke volume variation, stroke volume, stroke volume index, hypotension probability index, pulse rate, and systolic, diastolic and mean arterial pressure from the non-invasive arterial waveform.

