## **Level of significance**

The level of significance will be taken as  $p < 0.05$  and be corrected for repeated measurements

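### Linear regression on MAP at the LLA, and Bland-Altman for the limits, have no rule for limits MAP never crosses; dropping those patients biases mean LLA upwards and mean ULA downwards

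*Protocol*

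**What the plan says.** - **How a limit becomes visible.** Protocol section 1 describes a plateau, with blood flow roughly constant when perfusion pressure "is in the range between 50 and 150 mmHg" and pressure-dependent only outside it. MAP may stand in for perfusion pressure.
- **Who controls MAP.** Section 5.1 calls the study observational and non-randomised. Section 6 says "All treatment will be as per standard institutional care and none of the sensors will be used to guide treatment", apart from routine use of the FloTrac sensor. No pressure challenge is planned.
- **What is analysed.** Section 9.1.2 lists "Agreement between MAP at the upper and lower limits of renal autoregulation from invasive and non-invasive blood pressure measurement" as a secondary outcome, and the same for the brain. Section 9.4 names Bland-Altman as the agreement method. It also states "Multiple linear regression will be used to estimate the effect of demographic variables (age, gender", with medical history, preoperative blood pressure and other terms, ending in "time-averaged cerebral oximetry index characteristics on MAP at the LLA".
- **What happens to absent values.** "Missing data will be coded as missing and no imputation will be used" closes the bullets on descriptive variables and on intraoperative data. The regression and Bland-Altman bullets have no rule of their own.
- **What is deferred.** A full analysis plan is to follow, but the listed methods are to be part of it.

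**The concern.** If MAP never falls below a patient's LLA, the curve stays flat down to the lowest MAP recorded and no LLA can be read from it. Something is still known: the LLA lies below that MAP. The value is left-censored. By the same reasoning, a ULA that is never crossed is right-censored at the highest MAP.

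Ordinary linear regression needs a number for the outcome, so these patients leave the model. They are not a random subset: for a given lowest MAP, they are the ones with the lower LLAs. Limit agreement is likewise computed only where both devices yield a limit.

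At stake are the mean limits, the regression coefficients for the LLA and the limit-agreement secondary outcomes. The primary outcome (waveform data fit for algorithm development) and the agreement of the pressures themselves are not touched.

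**Working it through.** **Inputs.** The protocol gives 100 patients (section 9.2: "an estimate of 100 patients was made to start development"), with no LLA distribution, intraoperative MAP range or expected proportion of limits found. There is no plan figure to reproduce. All means and SDs below are assumptions, in mmHg, except the 50 and 150 taken from section 1.

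**1. Bias of the mean LLA.** Let LLA ~ N(μL, σL²) and lowest sustained MAP ~ N(μM, σM²), independent. The LLA is seen only if lowest MAP < LLA. With s = √(σL² + σM²) and z = (μL − μM)/s:

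- proportion identified = Φ(z)
- bias of the mean among those identified = (σL²/s) × φ(z)/Φ(z)

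Take σL = 12 and σM = 8, so s = √(144 + 64) = 14.42.

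- μL = 70, μM = 55: z = 1.040; identified 0.851; bias = 9.985 × 0.2323/0.851 = **+2.7**.
- μL = 60, μM = 65: z = −0.347; identified 0.364; bias = 9.985 × 0.3757/0.364 = **+10.3**.

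With μL = 50 (the section 1 figure), σL = 10 and μM = 55 to 65, the LLA is identified in 35% down to 12% of patients and the bias is +8.3 to +13.0.

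**2. Upper limit.** The mechanism is mirrored. With an assumed ULA mean of 100 (SD 10) and highest MAP of 100 (SD 8), 50% are identified and the mean is 6.2 too low. The yield depends heavily on the assumed ULA. With ULA SD 15 and highest sustained MAP 105-115 (SD 12), s = √(225 + 144) = 19.21:

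- ULA mean 150: Φ(−45/19.21) to Φ(−35/19.21), about 1 to 3 of 100 patients.
- ULA mean 110: Φ(−5/19.21) to Φ(5/19.21), about 40 to 60 of 100.

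**3. Predictor effects.** Simulated trials, n = 100: LLA = 60 + 8 × hypertension + N(0, 11), lowest MAP with mean 60 and SD 8, true effect 8. Hypertension was also allowed to raise lowest MAP.

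| Rise in lowest MAP with hypertension | Complete-case effect (true 8) |
|---|---|
| 0 | 5.0 |
| 4 | 6.5 |
| 8 | 8.1 |
| 12 | 9.7 |

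A second set-up (LLA mean 65, SD 10, true effect 5, mean lowest MAP 50-70) gave 2.9-4.1 when the predictor left lowest MAP unchanged, about 5.0 when it raised it by 5, and 5.6-6.2 when it raised it by 8. The upward bias of the mean LLA appeared in every scenario.

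**4. Bland-Altman on the limits** (true bias 0, SD of differences 8).

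- Constant within-patient device offset: bias 0.0, SD 8.0, so no distortion.
- Independent error in the non-invasive limit, both limits required: SD falls to 7.5-6.8, mean difference moves to +0.9 to +2.5, and 81% down to 28% of patients remain.

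**5. Does a censored model repair it?** In the first set-up of step 3, with hypertension unrelated to lowest MAP and 39% censored, complete-case regression gave mean LLA 70.2 and effect 4.9. A censored-normal (Tobit) fit gave 64.0 and 7.9; the truth is 64 and 8. This holds only if every unidentified limit was truly not reached. If 10/20/30% of reached limits go undetected for other reasons and all unidentified limits are treated as censored, the mean LLA becomes 62.0/59.7/57.1. Censoring only the curves that show a plateau down to the lowest MAP gives about 63 in the 20% case.

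**The case against.** **The handling of unreached limits belongs in the analysis plan still to be written.** This stands for the detail: how a limit is identified, and the rule for one that is not, are normal content of that plan. It does not cover the model. Section 9.4 already commits the plan to linear regression on an outcome that, by section 1, will be unobservable in some patients.

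**The no-imputation sentence is not about the limits.** Correct. A reader might infer that the protocol itself classes unreached limits as missing in the regression and Bland-Altman analyses, but the sentence belongs to the descriptive bullets. The exclusion follows from the choice of linear regression and from the absence of any other rule. A censored likelihood is not imputation, so the sentence does not forbid it.

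**Predictor effects need not shrink.** This stands. A reader might infer general attenuation, but that needs a predictor that moves lowest MAP less than it moves the LLA. Hypertension and preoperative MAP are in the model and may plausibly move both, so the direction cannot be told from the documents.

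**Agreement need not look better than it is.** This stands. With a constant device offset nothing changes. With independent error the limits of agreement narrow, but the mean difference moves away from zero.

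**Upper-limit agreement is not shown to be inestimable.** This stands. That reading takes 150 mmHg as the typical ULA, whereas section 1 offers it as part of a general concept. At 110 the yield is 40 to 60 of 100.

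**Censoring every unidentified limit replaces one bias with another.** This also stands. Sensor noise, too little time below the limit or impaired autoregulation can hide a limit that was reached. The remedy has to separate these cases.

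**Conclusion.** The point holds in limited form. Followed as written, section 9.4 estimates mean LLA and its predictors in patients selected for high LLAs, and any mean ULA in patients selected for low ULAs. The directions of bias in the two means follow from the protocol's own description of autoregulation together with unmanipulated MAP.

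The sizes do not follow from the protocol. The +2.7 to +10 mmHg range for mean LLA rests on the assumed distributions and on lowest MAP being independent of the LLA. The documents support no fixed direction for the predictor effects, no general claim that agreement is flattered, and no claim that ULA agreement cannot be estimated.

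The change should be made, because the fitted model does not suit its outcome and a better one needs no new data. It concerns secondary outcomes and a regression that is not itself a listed outcome, in a study whose primary outcome is the data.

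**What to change.** In section 9.4, or in the full analysis plan before data analysis:

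1. Classify each unidentified limit, by device and organ, as (a) not reached: the curve shows a plateau down to the lowest, or up to the highest, sustained MAP; or (b) not determinable: noise, too little data or no plateau. Define sustained MAP in advance.
2. Treat (a) as censored at that MAP (LLA left-censored, ULA right-censored) and (b) as missing.
3. Fit a censored-normal regression for MAP at the LLA and report the complete-case linear fit beside it.
4. Report the proportion of limits identified per device and organ, with the 2×2 table of found/not found by invasive versus non-invasive pressure.
5. Label Bland-Altman results for the limits as conditional on both being found, and keep ULA agreement descriptive if few are found.

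The cost is some wording, one standard model and a classification step applied to every curve. The downsides are a normality assumption for the censored part and some remaining bias. Misclassifying (a) and (b) adds bias, and even correct classification leaves a little, because (b) can include patients whose limit was reached (mean LLA about 63 against 64 in the 20% case).

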### **4.3 Number and source of patients and participants .**

100 patients undergoing major non cardiac surgery will be recruited – 50 from each participating site.

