## **5. Allocation**

### **5.1 Allocation to treatment**

This will be a prospective non randomised observational study recruiting 50 sequential patients at both sites. There is no allocation to treatment and all subjects will receive standard institutional care.

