### **6.1 Anaesthetic technique.**

Anaesthetic technique will be at the discretion of the anaesthetist as per the current practice at the host institution.

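### The regression for MAP at the lower limit of autoregulation lists its covariates without study site, so patient-factor effects may be confounded with centre and the listed model could not tell the two apart

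*Protocol*

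**What the plan says.** Protocol section 9.4 describes the model in one sentence. It begins "Multiple linear regression will be used to estimate the effect of demographic variables (age, gender), medical history (diabetes, hypertension, and prior cerebrovascular accident" and continues "preoperative blood pressure (MAP, systolic blood pressure, pulse pressure), and time-averaged cerebral oximetry index characteristics on MAP at the LLA". If the oximetry index enters as one term, that makes nine covariates: age, gender, diabetes, hypertension, prior cerebrovascular accident, three preoperative pressures and the index. Site is not one of them, and no other section adjusts for or stratifies by site.

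The design has two centres. Section 4.3 states: "100 patients undergoing major non cardiac surgery will be recruited – 50 from each participating site". Section 4.1 leaves the need for invasive arterial monitoring, and so eligibility, to the treating clinician. Section 5.1 states: "There is no allocation to treatment and all subjects will receive standard institutional care". Section 6.1 adds: "Anaesthetic technique will be at the discretion of the anaesthetist as per the current practice at the host institution".

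Section 9.4 introduces its list with "A full analysis plan will be written prior to data analysis however will include". Section 9.2 gives no power or precision basis for the sample size, saying only that "an estimate of 100 patients was made to start development".

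**The concern.** The model is meant to estimate effects of patient factors on the LLA in a non-randomised study, so the choice of adjustment variables decides how the coefficients can be read. Two conditions must hold together for centre to confound them. The factor must be more common at one hospital, and the LLA must differ between hospitals after the listed covariates are allowed for.

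The protocol makes both plausible. Entry depends on local decisions about arterial lines, and nothing balances case mix between a UK hospital and a Dutch university centre. Technique and other care follow each institution. Section 9.4 has fluids, vasoactive drugs, epidural use and type of surgery recorded, but none of these enters the regression. Site is the simplest available stand-in for such differences.

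If both conditions hold, a centre difference could be reported as an effect of, say, hypertension or age, and the false-positive rate would exceed the stated 5%. If case mix is balanced but the LLA differs by centre, leaving site out costs some precision and causes no bias.

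**Working it through.** **The plan's own figure.** 2 sites × 50 = 100 patients, which agrees with sections 4.3 and 9.2. The protocol gives no SD, site difference or prevalence, so everything below rests on assumed values.

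**Assumptions.** One binary factor with no true effect; 50 patients per site, all with an LLA; within-site SD of the LLA 12 mmHg; two-sided 5% test; site difference d of 4, 8 or 10 mmHg; factor prevalence p1 and p2 at the two sites.

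**Bias when site is left out.** Bias = d × slope of site on the factor. With equal site sizes and mean prevalence p = (p1 + p2)/2, the slope is 0.25 × (p2 − p1) / [p(1 − p)].

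- 30% vs 60%: 0.25 × 0.30 / (0.45 × 0.55) = 0.303.
- 40% vs 60%: 0.25 × 0.20 / (0.50 × 0.50) = 0.200.
- Equal prevalence: 0.

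**Type I error, one case by hand (30% vs 60%, d = 8).** Bias = 8 × 0.303 = 2.42 mmHg. The squared correlation of site and factor is 0.303 × 0.30 = 0.091. The residual variance without site is 144 + 64 × 0.25 × (1 − 0.091) = 158.5, so the SD is 12.6. The standard error is 12.6 / √(100 × 0.2475) = 2.53. The shift is 2.42 / 2.53 = 0.96 standard errors, and the chance of exceeding ±1.98 is about 15%.

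**All cases.** Type I errors are from simulation, 6,000 runs per case; a repeat run agreed to within about one percentage point.

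| Prevalence | d (mmHg) | Spurious effect (mmHg) | Type I error, no site term |
|---|---|---|---|
| 40% vs 60% | 4 | 0.8 | about 7% |
| 40% vs 60% | 8 | 1.6 | about 10% |
| 40% vs 60% | 10 | 2.0 | about 12% |
| 30% vs 60% | 4 | 1.2 | about 8% |
| 30% vs 60% | 8 | 2.4 | about 15% |
| 30% vs 60% | 10 | 3.0 | about 22% |
| equal at both sites | any | 0 | about 5% |
| any | 0 | 0 | about 5% |

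With site in the model, the bias is about 0 and the type I error about 5% throughout. A separate simulation with SD 10 mmHg and d = 5 gave 7.4% (40% vs 60%) and 16.8% (30% vs 70%) without site, and 4.7% to 4.8% with it.

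**Cost of the extra term.** Going from 9 to 10 covariates takes residual degrees of freedom from 100 − 9 − 1 = 90 to 89, and the critical t from 1.9867 to 1.9870. Variance inflation for the factor is 1 / (1 − squared correlation): 1.00 when balanced, 1 / (1 − 0.2 × 0.2) = 1.04 for 40% vs 60%, and 1 / (1 − 0.091) = 1.10 for 30% vs 60%.

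For a true effect of 6.8 mmHg and no site difference, simulated power without and with site was 0.799 and 0.796 (45% at both sites), 0.790 and 0.774 (40% vs 60%), and 0.792 and 0.747 (30% vs 60%). With balanced prevalence, adding site changed power by about 0, +4 and +5 points for d = 4, 8 and 10 mmHg.

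**The case against.** The strongest reply is that section 9.4 is an outline. It promises a full analysis plan, and its wording does not forbid further terms. On this view the sentence lists the effects of interest, and a centre adjuster is the kind of detail a later plan supplies. This stands in part: site can still be added without contradicting the protocol. But the protocol did not leave this model open. It named the outcome and an explicit set of covariates, and that set as written does not deal with centre.

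A reader might infer that the effects are confounded with centre, or that the 50/50 enrolment causes it. The documents support neither. They report no difference between the hospitals in case mix or LLA, and equal enrolment does not create confounding.

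Three further limits stand:

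- The illustration has one factor, whereas the protocol's model has about nine terms. Age, hypertension and the preoperative pressures may absorb part of a case-mix difference.
- If fewer than 100 patients yield an LLA, the standard error is larger and the same bias inflates type I error less.
- Section 6.1 also gives discretion to the individual anaesthetist, and a site term does not remove variation in technique within a hospital.

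**Conclusion.** The point holds as a possibility that the listed model cannot rule out. Patient-factor effects on MAP at the LLA may be confounded with centre, and without a site term the two cannot be separated. The range of about 0.8 to 3 mmHg and 7% to 22% type I error depends wholly on the assumed SD, prevalences and site differences. Its upper end needs both a 30% vs 60% imbalance and a 10 mmHg site difference.

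The reach is limited. A reader might infer that the study's main results are at risk, but the primary outcome (section 9.1.1) is data suitable for building curves and algorithms, and the secondary outcomes (section 9.1.2) are agreement measures. The regression serves none of these, and the sample size was not set for it. This is a cheap improvement to a supporting analysis, worth making before the data are analysed.

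**What to change.** In section 9.4, and in the full analysis plan, add site (York / Groningen) as a fixed covariate in the multiple linear regression for MAP at the LLA, so that patient-factor effects are estimated within site. With only two sites, a random site effect is not workable.

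Site is known for every patient, so no extra data are needed. The price is one degree of freedom and slightly wider intervals for factors whose prevalence differs by site. In the cases above, the worst loss is about 5 power points, when prevalence is 30% vs 60% and the sites do not in fact differ in LLA. Naming the term before analysis also keeps the choice from depending on the data.

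### The regression for MAP at the lower limit enters preoperative MAP, systolic pressure and pulse pressure together, so their separate coefficients cannot be estimated or are very imprecise; at most two should be kept

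*Protocol*

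**What the plan says.** Protocol section 9.4 says that a full analysis plan will follow but already lists what it will contain. One item is a single regression: "Multiple linear regression will be used to estimate the effect of demographic variables (age, gender), medical history" and, in the same sentence, "preoperative blood pressure (MAP, systolic blood pressure, pulse pressure), and time-averaged cerebral oximetry index characteristics on MAP at the LLA". The history items are diabetes, hypertension and prior cerebrovascular accident. No selection step, alternative covariate set or rule for collinear terms is given.

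Three other statements bear on the point.

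- The baseline pressures to be collected are "baseline systolic, diastolic and mean blood pressure" (section 9.4). Pulse pressure is not among them, so it has to be derived as systolic minus diastolic.
- Section 6 has monitor 1 report "systolic, diastolic and mean arterial pressure from the invasive arterial waveform", with ten minutes of baseline recording before induction. The protocol does not say whether preoperative MAP is this waveform value, a cuff value or a calculated one.
- On the outcome, section 9.4 says "Cerebral and renal autoregulation curves will be created using invasive mean arterial pressure as a substitute of cerebral/renal perfusion pressure" and "Cerebral/renal oxygenation will be used as a surrogate of blood flow". It defines neither the cerebral oximetry index nor the rule for reading the lower limit from the curve. I read LLA as the lower limit of cerebral autoregulation; the protocol does not spell the abbreviation out.

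**The concern.** The stated purpose is to estimate effects, so each coefficient is meant to be read on its own. A systolic coefficient in this model is the change in the lower limit per mmHg of systolic pressure with MAP and pulse pressure held fixed. Once those two are fixed, systolic pressure has almost no room to move. What room there is comes from the departure of measured MAP from the usual formula, that is, from waveform shape and measurement error. With a calculated MAP there is none, and software will drop a term or return an arbitrary solution.

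The preoperative pressure effects would therefore be uninformative, and a non-significant or wrong-signed coefficient could be reported as a result about blood pressure.

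A second, softer matter concerns the index. The outcome is read from a curve with cerebral oxygenation on one axis, and the index is also a cerebral oximetry quantity. Some of their association may come from shared source data, and adjusting for the index may change what the patient-factor coefficients mean.

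**Working it through.** The protocol gives no effect size, SD or precision for this regression, so there is no stated figure to reproduce. The SDs, the correlations and the error in MAP below are assumptions, shown as ranges.

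**Step 1. Calculated MAP.** Let S, D and P be systolic, diastolic and pulse pressure.

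- P = S − D.
- Formula MAP: M* = D + P/3 = S − (2/3)P.

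M*, S and P have rank 2. With an intercept the design has rank 3 of 4, which a numerical check confirms.

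**Step 2. Measured MAP.** Write M = M* + e, with e independent and of SD 2 to 8 mmHg. Take SD(S) = 20, SD(D) = 11 and correlation 0.6, so Cov(S, D) = 0.6 × 20 × 11 = 132.

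- Var(M*) = 400/9 + 4 × 121/9 + 4 × 132/9 = 156.9
- Var(P) = 400 + 121 − 2 × 132 = 257
- Cov(M*, P) = (400 + 132 − 2 × 121)/3 = 96.7
- Var(M* given P) = 156.9 − 96.7²/257 = 120.5

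Since S = M* + (2/3)P, the variance left in S once M and P are known is 120.5 × e²/(120.5 + e²).

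- SD of e = 2: 120.5 × 4/124.5 = 3.87. Variance inflation factor (VIF) = 400/3.87 = 103. Its square root is 10.2.
- SD of e = 8: 120.5 × 64/184.5 = 41.8. VIF = 400/41.8 = 9.6. Its square root is 3.1.

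Over correlations of 0.5 to 0.7:

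| SD of e (mmHg) | VIF MAP | VIF systolic | VIF pulse pressure | SE multiplier, systolic | VIF, MAP and pulse pressure only |
|---|---|---|---|---|---|
| 2 | 38–43 | 103 | 27–37 | 10.2 | 1.2–1.4 |
| 3 | 17–20 | 48 | 14–18 | 6.9 | 1.2–1.4 |
| 5 | 6.9–7.7 | 19 | 7.2–8.7 | 4.4 | 1.2–1.4 |
| 8 | 3.3–3.6 | 9.6–9.7 | 4.9–5.4 | 3.1 | 1.1–1.3 |

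Moving the SDs to 18 and 10 (correlation 0.5) or to 22 and 12 (correlation 0.7) gives a systolic VIF of 84 to 124 at 2 mmHg and 8 to 11 at 8 mmHg. The conclusion does not change.

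**Step 3. What this means with 100 patients.** The sentence names at least nine terms: age, sex, three history items, three pressures and at least one index term. Simulated data used n = 100, residual SD 10 mmHg (assumed), the Step 2 SDs and correlation, and e with SD 3.

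| Coefficient | SE, three pressures | SE, MAP and pulse pressure |
|---|---|---|
| MAP (mmHg per mmHg) | 0.35 | 0.092 |
| Systolic | 0.37 | not in model |
| Pulse pressure | 0.26 | 0.074 |
| Age (mmHg per year) | 0.087 | 0.087 |
| Hypertension (mmHg) | 2.09 | 2.08 |

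A 95% interval for 10 mmHg of systolic pressure is about ±10 × 1.96 × 0.37 = ±7 mmHg. For 10 mmHg of MAP in the reduced model it is ±10 × 1.96 × 0.092 = ±1.8 mmHg.

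The age and history terms barely move. This follows from the algebra: the three pressures span the same space as M*, P and e, so including all three only adds e to the adjustment.

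**Step 4. The index.** The lower limit comes from invasive MAP and cerebral oxygenation; the index, by its name, comes from cerebral oximetry. The shared signal is in the text. How strongly it couples index and outcome cannot be calculated without definitions that the protocol does not give.

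**The case against.** **The model may be full rank.** A reader might infer from the list of predictors that the coefficients will be undefined. The protocol does not support that. Exact dependence needs a calculated MAP; the source of preoperative MAP is not stated, and section 6 has a monitor reporting MAP from the waveform. With a measured MAP the model can be fitted. This objection stands against the word undefined but not against the point: even at 8 mmHg of departure the systolic standard error is about three times what it would be without collinearity.

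**The damage is local.** One might infer that the whole regression is compromised. It is not. Step 3 shows that the other coefficients are unaffected, and the fitted values do not suffer either. This stands.

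**The index is not shown to be circular.** It is tempting to say that the index is a consequence of the outcome and must come out. Neither the index nor the rule for the limit is defined. A simulation that sets the index high below the limit and low above it builds in the coupling it is meant to measure, with inputs absent from the protocol. The text supports shared source data and no more. I therefore attach no size to this part and do not propose deleting an association that the protocol plans to examine.

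**Site is absent from the model.** Recruitment is "50 from each participating site", and a reader might count the missing site term as an error. Adding it is ordinary detail for the analysis plan and would contradict nothing here, so it is not part of this point.

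**A later plan could repair this.** It could, but a plan that followed section 9.4 would inherit the redundancy, and one that dropped a pressure would depart from the protocol.

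**Conclusion.** The sentence is wrong as written, at moderate weight. Three pressures with essentially two dimensions are entered in one model. If MAP is calculated, their separate coefficients cannot be estimated. If MAP is measured and departs from the formula by SD 2 to 8 mmHg, the systolic VIF is about 10 to 103 and its standard error about 3 to 10 times larger; MAP and pulse pressure alone have a VIF of about 1.1 to 1.4. These figures rest on an assumed systolic SD of 20, diastolic SD of 11 and correlation of 0.5 to 0.7. The rank result for calculated MAP rests on algebra alone.

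The effect is confined to the three pressure coefficients. The possible coupling of index and outcome is a matter for careful reporting, not a demonstrated bias. The primary outcome in section 9.1.1 is data suitable for curves and pilot algorithms, and the secondary outcomes in section 9.1.2 are agreement measures, so neither depends on this regression. That is why a stronger rating is not justified.

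**What to change.** In section 9.4, or in an analysis plan that states the departure from it:

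1. Keep at most two of the three preoperative pressures, for example MAP and pulse pressure. That pair is the least correlated: at correlation 0.6 and e of SD 2 to 8 its VIF is 1.2 to 1.3, against 2.2 to 4.2 for MAP with systolic and 3.3 for systolic with pulse pressure (each 1/(1 − r²)).
2. Report the effects of age, sex, medical history and preoperative pressure from a model without the oximetry-index terms.
3. Present the model with the index terms as a secondary association, noting that index and limit both rest on the cerebral oximetry signal and that the association may reflect this.

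The cost is that no separate systolic coefficient is reported and one extra model is fitted. If MAP is calculated, any two of the pressures give the same fitted values as all three, so nothing is lost. If it is measured, what is lost is only the part of MAP that departs from the formula. No new data are needed.
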